10.1.1 Study sites

The program will be available to select hospitals approved by Indian regulatory authority with access to Praxbind™.

Hospital (sites) having access to Praxbind™ will receive information material about Praxbind™ administration surveillance program.

10.1.2 Study population

The target population will be all patients, who receive Praxbind™ prescribed as per the approved label.

The patients who participate in 1160.189 and 1160.248 study and have a requirement for Praxbind™ will also be part of this protocol.

Inclusion criteria:

1. Patients treated with Pradaxa (dabigatran etexilate) capsules with requirement of rapid reversal of the anticoagulant effects of dabigatran:
 - For emergency surgery/urgent procedures
(or)
 - In life-threatening or uncontrolled bleeding
2. Written informed consent in accordance with International Conference on Harmonization Good Clinical Practice (GCP) guidelines and local legislation and/or regulations.

Exclusion criteria:

- Participation in a Praxbind™ clinical trial.

10.1.3 Study discontinuation

A log of all patients included into the drug surveillance study will be maintained at the Investigational sites.

Boehringer Ingelheim reserves the right to discontinue the study overall or at a particular study site at any time for the following reasons:

1. Emergence of any efficacy/safety information of PraxbindTM that could significantly affect continuation of the study.
2. Violation of the study protocol, or the contract by a study site or investigator, disturbing the appropriate conduct of the study

The investigator / the study site will be reimbursed for reasonable expenses incurred in case of study termination.

10.2 VARIABLES

1. Site characteristics:

To evaluate the diversity of sites the following information will be collected for each participating site:

- Multi-specialty hospitals with emergency management facilities and having access to PraxbindTM
- Practice type (academic, non-academic, private, Government)
- Availability of prescription/medical records at the site.

Patient characteristics and PraxbindTM use:-

The following anonymized data will be collected from the PraxbindTM administration records upon availability:

2. Patient Data:

- Year of Birth
- Gender: Male or Female
- Vital Signs
- Physical Examination
- Laboratory data (Data would be collected of lab results performed as a routine practice. No additional lab tests should be performed specifically for this study purpose)
- Pregnancy status in case of female patient

3. Medical History:

- Name, dose and last intake of previous anticoagulant medications (Dabigatran);

- Pertaining to haemorrhagic risk factors or impact on safety outcomes (e.g. renal impairment, congenital or acquired coagulation disorders, thrombocytopenia or functional platelet defects, recent biopsy, recent surgery, major trauma, bacterial endocarditis, esophagitis, gastritis, gastroesophageal reflux, hepatic disorders, vascular disorders, neoplasms/cancer, inherited vascular disorder (aneurysms, arteriovenous malformation, microangiopathy) and the HAS-BLED score).
- Concomitant treatment pertaining to haemorrhagic risk factors or impact on safety outcomes (e.g. acetylsalicylic acid, non-steroidal anti-inflammatory drugs, clopidogrel, selective serotonin reuptake inhibitors or serotonin–norepinephrine reuptake inhibitors, Strong P-Gp inhibitors (e.g. ketoconazol, clarithromycin, ticagrelor), chemotherapy, radiation therapy).

4. PraxbindTM utilization:

- Department (emergency, operating room, ICU, other patient setting);
- Type of surgery /procedure if applicable;
- Information on bleeding event including location (Gastrointestinal tract; Intracranial; Skin, Urogenital tract, Intramuscular, Retroperitoneal, Undefined location, Other (defined location) if applicable, and if bleeding was life-threatening (yes/no);
- Indication: life-threatening or uncontrolled bleeding requiring urgent medical intervention, emergency surgery or other urgent medical procedure necessitating rapid reversal of the anticoagulant effect of dabigatran prior to surgery/procedure, scheduled or planned surgery/procedure, other;
- Dosage and administration (total dose administered and time interval between the administration of the two vials; vials to be taken one after the other, immediate administration of the second vial is mandatory);
- Premature PraxbindTM administration discontinuation (yes/no).
- In case if the patient requires an additional 5 g dose for the following conditions as per the label:
 - i. recurrence of clinically relevant bleeding together with prolonged clotting times, or
 - ii. if potential re-bleeding would be life-threatening and prolonged clotting times are observed, or
 - iii. patients require a second emergency surgery/urgent procedure and have prolonged clotting times.
- Information on restart of anticoagulation therapy (which anticoagulation treatment including dose and when was it restarted).
- All adverse drug reactions (ADRs, serious and non-serious) associated with PraxbindTM.
- All AEs with fatal outcome in patients exposed to PraxbindTM.

10.2.1 Exposures

Not Applicable

10.2.2 Outcomes

10.2.2.1 Primary outcomes

Any suspected ADRs and fatal AEs; with special focus on hypersensitivity and thrombotic event, occurred within 7 days after PraxbindTM administration.

10.2.2.2 Secondary outcomes

Percentage of patients who either received PraxbindTM for emergency surgery/urgent procedures or in life-threatening or uncontrolled bleeding at the end of 2 years.

10.2.3 Covariates

Not Applicable

10.3 DATA SOURCES

Data collected from patient's medical notes and hospital records will be entered by the site directly in the paper based forms. All sites will be fully trained for using the CRF forms. It is the site's responsibility to ensure the accuracy of the data provided to the program by any site staff that is trained for the program data collection. The program does not entail any change in prescribing pattern or management policies which are left to the discretion of the treating physician. No special evaluation procedure is required. The data to be entered in the e-CRFs is part of the information that should be generally available during routine medical practice.

Data will be transferred to the Sponsor after closure of the program.

10.4 STUDY SIZE

This program will be initiated after the commercial availability of PraxbindTM in India. It will include up to 25 patients who require PraxbindTM according to the approved Indian label or the patients included in 2 years at selected Centers approved by the regulatory authority, whichever is earlier.

10.5 DATA MANAGEMENT

A data management plan will be created before data collection begins and will describe all functions, processes, and specifications for data collection and validation.

10.6 DATA ANALYSIS

10.6.1 Main analysis

A detailed analysis plan will be prepared prior to First Patient In.

All variables will be presented using descriptive statistics (absolute and relative frequencies, means, standard deviations, medians, quartiles, minimum and maximum values, 95% CIs) as appropriate for the nature of the variables (i.e. categorical or continuous).

10.7 QUALITY CONTROL

It is the responsibility of the Investigator to ensure that the data are as accurate and complete as possible. The Investigator and delegate will be trained on data entry.

Data will be recorded by local site staff directly into the e-CRF's. Data quality will be ensured by implementation of validations and edit checks.

No patient identifying information will be available to non-study staff except Ethics Committee and regulatory agencies during inspections.

10.8 LIMITATIONS OF THE RESEARCH METHODS

This study will include only up to 25 consecutive patients who require PraxbindTM. The data analysis will be done using descriptive statistics with no formal statistical hypothesis.

10.9 OTHER ASPECTS

10.9.1 Data quality assurance

A quality assurance audit/inspection of this study may be conducted by the sponsor or sponsor's designees or by Institutional Review Board (IRBs) / Independent Ethics Committee (IECs) or by regulatory authorities. The quality assurance auditor will have access to all medical records, the investigator's study-related files and correspondence, and the informed consent documentation of this study.

10.9.2 Study records

Case Report Forms (CRFs) for individual patients will be provided by the sponsor electronically.

10.9.2.1 Source documents

Source documents provide evidence for the existence of the patient and substantiate the integrity of the data collected. Source documents are filed at the investigator's site.

Data reported on the e-CRFs that are transcribed from source documents must be consistent with the source documents or the discrepancies must be explained. The investigator may need to request previous medical records or transfer records, depending on the study; also current medical records must be available.

For e-CRFs, the following data need to be derived from source documents:

- Patient identification (gender, date of birth)
- Patient participation in the study (product, study number, patient number, date patient was informed)
- Dates of Patient's visit, (including Praxbind™ administration & Hospital Admission details)
- Medical history (including indication and concomitant diseases, if applicable)
- Medication history
- Adverse events (onset date (mandatory), and end date (if available))
- Serious adverse events (SAEs) (onset date (mandatory), and end date (if available))
- Concomitant therapy (start date, changes)
- Laboratory results
- Conclusion of Patient's Participation in the study

10.9.2.2 Direct access to source data and documents

The Investigator / institution will permit active surveillance study related monitoring, audits, IRB/IEC review and regulatory inspection, providing direct access to all related source data/documents.

e-CRF and all source documents, including progress notes and copies of laboratory and medical test results must be available at all times for review.

The Clinical Research Associate (CRA)/ on site monitor and auditor may review all e-CRF and written informed consents.

10.9.2.2.1 Storage of records

Site(s)

The trial site(s) must retain the source and essential documents (including ISF) according to the national or local requirements (whatever is longer) valid at the time of the end of the trial.

Sponsor

The sponsor must retain the essential documents according to the sponsor's SOPs.

11. PROTECTION OF HUMAN SUBJECTS

The study will be carried out in compliance with the protocol, the principles laid down in the Declaration of Helsinki, in accordance with the ICH Harmonized Tripartite Guideline for Good Clinical Practice (GCP) (to the extent applicable to the NIS setting and required by local regulations), Good Epidemiological Practice (GEP), Guidelines for Good Pharmacoepidemiology Practice (GPP), and relevant BI Standard Operating Procedures (SOPs). Standard medical care (prophylactic, diagnostic and therapeutic procedures) remains in the responsibility of the treating physician of the patient.

The investigator should inform the sponsor immediately of any urgent safety measures taken to protect the study subjects against any immediate hazard, and also of any serious breaches of the protocol/ICH GCP.

The rights of the investigator and of the sponsor with regard to publication of the results of this study are described in the investigator contract. As a general rule, no study results should be published prior to finalization of the Study Report.

11.1 STUDY APPROVAL, PATIENT INFORMATION, AND INFORMED CONSENT

In addition to review and approval by Drug controller general of India (DCGI), the approval of Institutional Review Board (IRB) or Ethics Committee will be sought as per the institutional procedures before the start of this active surveillance.

Prior to patient participation in this active surveillance study, written informed consent must be obtained from each patient (or the patient's legally accepted representative) according to the regulatory and legal requirements of India. Each signature must be personally dated by each signatory and the informed consent and any additional patient-information form retained by the Investigator as part of the study records. A signed copy of the informed consent and any additional patient information must be given to each patient or the patient's legally accepted representative.

The Investigator must give a full explanation to the participants of this active surveillance regarding the collection of the safety data at specific time points. The Investigator obtains written consent of the patient's own free will with the informed consent form after confirming that the patient understands the contents. The Investigator must sign and date the informed consent form.

The patient must be informed that his/her personal study-related data will be used by Boehringer Ingelheim in accordance with the local data protection law. The level of disclosure must also be explained to the patient.

The patient must be informed that his / her medical records may be examined by authorized monitors (CML/CRA) or Quality Medicine auditors appointed by Boehringer Ingelheim, by appropriate IRB / IEC members, and by inspectors from regulatory authorities.

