10. RESEARCH METHODS

This program will be initiated after the commercial availability of Praxbind™ in India. It will include patients administered with Praxbind™ into the surveillance program after commercial availability in 2 years at selected centers approved by the regulatory authority.

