10.1 STUDY DESIGN

This is a post marketing surveillance study wherein patients will be eligible for the study if they are prescribed Praxbind™ as per the approved label. The drug administration surveillance program is designed as a multi-center program enrolling patients administered with Praxbind™. Data will be collected for patients who have been treated with Praxbind™ within 2 years. There are no protocol mandated follow-up visits or procedures associated with the program. No interference with usual medical care is involved, and thus it will not affect the treatment of patients.

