### **7.3 PATIENT SETS ANALYSED**

➤ **Screened Set:**

Screened set includes all patients who signed the ICF.

➤ **Entered Set:**

Entered set includes patients in screened set who met the eligibility criteria.

➤ **Treated Set:**

Patients in entered set who have received the study drug Praxbind™.

Analysis for all primary and secondary outcomes will be done on treated analysis set.

The following table defines the patient set is to be used for planned analysis.

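### Consent wording in Protocol 11.1, entry after dosing and event collection from consent put the 7-day fatal-AE percentage at risk of understatement, by an amount the documents cannot fix

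*Protocol*

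**What the plan says.** **Who consents.** Protocol 11.1 states that "written informed consent must be obtained from each patient (or the patient's legally accepted representative") under Indian requirements, and provides for handing the representative a signed copy. Its next paragraph has the investigator obtain the patient's own, freely given written consent "after confirming that the patient understands the contents". The representative does not appear there. Inclusion criterion 2 in Protocol 10.1.2 asks for "Written informed consent in accordance with International Conference on Harmonization Good Clinical Practice (GCP) guidelines and local legislation and/or regulations" and is silent on representatives and on timing.

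**When patients enter.** Protocol 10: "It will include patients administered with Praxbind™ into the surveillance program after commercial availability". Protocol 10.1: "Data will be collected for patients who have been treated with Praxbind™ within 2 years". Protocol 10.4 is looser: "It will include up to 25 patients who require PraxbindTM according to the approved Indian label". Section 11.1 places consent before participation, and participation is not tied to dosing.

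**What is counted.** Protocol 12.2 starts collection of ADRs and fatal AEs at the consent signature. The primary outcome (Protocol 10.2.2.1, SAP 6.1) covers events within 7 days after administration. In SAP 7.3, "Screened set includes all patients who signed the ICF". The Entered Set is drawn from the Screened Set and the Treated Set from the Entered Set. Primary and secondary outcomes are analysed on the Treated Set.

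**Safeguards.** The site log in Protocol 10.1.3 covers included patients only. Protocol 10.8 mentions only the small size and the absence of a hypothesis. The ENCePP checklist (item 12.1.1) says selection bias is discussed in 10.9, but that section deals with audit and records. Item 7.2.1 answers No on selection bias.

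**The concern.** The drug is given for emergency surgery and life-threatening or uncontrolled bleeding, and intracranial bleeding is one of the recorded locations. Some of these patients will foreseeably be unable to understand a form, and dosing may come before anyone is approached. Fatal AEs within 7 days are part of the primary outcome. If being counted depends on someone signing after the dose, the earliest deaths can drop out of numerator and denominator together. The abstract gives the target population as all patients who receive the drug on prescription (10.1.2 limits this to on-label use), but the analysed population would be those for whom consent was obtained. Sites that read 11.1 differently could also enrol different kinds of patient. With no log of treated patients who were not enrolled, nobody could tell afterwards how many were missed.

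**Working it through.** **There is no plan figure to reproduce.** The 25 in Protocol 10.4 is a cap. It has no derivation, and the documents give no fatality rate, consent delay or incapacity rate. The first two steps below rest on text alone. The arithmetic uses assumed inputs.

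**Step 1: who can sign.** Section 11.1 provides for a representative twice (signature and copy). The later sentence on free will and understanding names only the patient. If that sentence covers only patients who sign for themselves, an incapacitated patient can enter through a representative. If it applies to every consent, that patient cannot enter. The text does not say which, and criterion 2 does not settle it.

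**Step 2: the path of an early death.** Dosing may precede consent (10, 10.1). Collection begins at consent (12.2). The Treated Set is nested in patients with a signed form (SAP 7.3). No deferred or post-death consent is described. A patient dosed, then dead before a signature, falls inside the 7-day window but has no described route into any analysis set. In addition, a non-fatal ADR between dosing and consent, such as an early hypersensitivity reaction, lies outside the collection period even in a patient who later enrols.

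**Step 3: deaths before consent (illustration).** Let p be the true 7-day fatality among all treated patients and f the share of those deaths before consent. Then

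observed = p(1 − f) / (1 − pf).

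With p = 10% (assumed) and n = 25:

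| f | Calculation | Observed | Expected deaths in 25 | Chance of no death in 25 |
|---|---|---|---|---|
| 0 | 0.10/1 | 10.0% | 2.5 | 7% |
| 0.10 | 0.09/0.99 | 9.1% | 2.3 | 9% |
| 0.25 | 0.075/0.975 | 7.7% | 1.9 | 13.5% |
| 0.50 | 0.05/0.95 | 5.3% | 1.3 | 26% |

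At f = 0.50, p = 5% gives 0.025/0.975 = 2.6% and p = 20% gives 0.10/0.90 = 11.1%. The relative shortfall is f(1 − p)/(1 − pf), which is close to f itself. The result therefore largely returns whatever f is assumed.

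**Step 4: incapacitated patients left out (illustration).** Let q be their share and R their fatality relative to capable patients. Fatality among capable patients is p/(1 − q + qR). With p = 10% and q = 0.25: R = 1 gives 10.0%, R = 2 gives 0.10/1.25 = 8.0%, and R = 3 gives 0.10/1.50 = 6.7%. The shift is downward only if R exceeds 1.

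**Step 5: scale.** The exact 95% confidence interval is 0 to 13.7% for 0/25 and 1.0% to 26.0% for 2/25. Sampling error is as large as most of these shifts.

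**The case against.** The strongest reply is that 11.1 plainly admits representatives, so the later sentence should be read as describing patients who sign for themselves. On that reading incapacitated patients are not excluded. Entry after dosing is permitted but not required, and the wording about patients who require the drug can describe the same people as the wording about patients who were given it. If consent precedes dosing and representatives sign, the bias is zero. In a descriptive study of at most 25 patients, the interval around the percentage is wide in any case.

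Much of this stands. A reader might infer that the consent criterion contradicts itself. It does not: criterion 2 is silent, and the tension lies inside 11.1. A reader might also infer that incapacitated patients are screened out and that the fatal-AE result is biased low as a matter of fact. The documents support neither, because both depend on how sites read 11.1 and on when consent is taken. The same holds for a shift in the indication mix of the secondary outcome: the documents give nothing from which to derive it.

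Two parts of the reply fail. A wide confidence interval does not cover a selection effect. And nothing in the plan makes consent precede dosing, so the gap between a window that opens at administration and collection that opens at consent remains on any reading.

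SAP Table 6.2: 1 lists missing consent (code A2.1) as a violation excluded from no set. A reader might take this to keep non-consented patients in the analysis. SAP 7.3 does not allow that, since its widest set already requires a signed form. The two entries need reconciling.

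**Conclusion.** The point holds as a risk. As written, treated patients who die before consent are not counted, and incapacitated patients may be left out at sites that read the later sentence of 11.1 literally. For deaths before consent the direction can only be downward. For incapacity it is downward only if those patients have higher fatality.

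The size is unknown. At an assumed true risk of 10% the expected figure runs from 10% (no deaths before consent) through 9.1% (a tenth) to 5.3% (half). This range illustrates the mechanism and does not estimate the bias. It is worth correcting because fatal AEs are in the primary outcome, no log or stated limitation offsets the problem, and the changes are small.

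**What to change.** 1. **Protocol 11.1:** extend the later sentence so that free consent and confirmed understanding apply to the patient or, where the patient lacks capacity, to the legally accepted representative.
2. **Protocol 10.1.2:** state when consent may be obtained relative to dosing, and keep the on-label inclusion criteria unchanged. Whether consent may be sought for a patient who has died is for the ethics committee and DCGI to decide. The documents cannot settle it.
3. **Protocol 12.2:** once consent is given, collect ADRs and fatal AEs back to Praxbind administration, so that collection matches the primary window.
4. **Protocol 10.1.3:** extend the site log to an anonymous count of treated but not enrolled patients, with the reason, where permitted. This is the only item that shows how many were missed.
5. **SAP 8.4:** summarise the interval from administration to consent. Signatures are personally dated (11.1) and administration dates are source data (10.9.2.1).
6. **Protocol 10.8 and the report:** state that the fatal-AE percentage applies to patients for whom consent was obtained and, where consent followed dosing with no post-death route, to those who survived to consent.
7. **SAP Table 6.2: 1:** reconcile code A2.1 with the set definitions in SAP 7.3.

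The cost is a wording amendment with ethics-committee notification, a short log and one extra summary. Two limits remain: the interval exists only for enrolled patients, and dates without times may not show whether same-day consent came before or after dosing.
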